**Mechanical Temporal Summation.** Temporal summation of pain will be assessed using repetitive mechanical stimuli. The assessment of temporal summation involves rapidly applying a series of identical noxious stimuli and determining the increase in pain across trials; animal studies have suggested that temporal summation occurs centrally in second-order neurons in the spinal cord as a consequence of sustained C-fiber afferent input (149-151). For temporal summation of mechanical pain, pain ratings in response to a single punctate noxious stimulus will be compared to pain ratings in response to a sequence of identical punctate noxious stimuli (152). A weighted pinprick stimulator with a flat contact area will be used to deliver either a single pinprick stimulus or a train of 10 pinprick stimuli repeated at a constant rate. Following the single stimulus and the 10-stimulus train, the subject is asked to give a pain rating. Single pinprick stimuli are alternated with the trains of 10 stimuli. Similar procedures using this type of weighted pinprick stimulator have been used in diabetic neuropathy (153), healthy subjects (154), and to assess temporal summation (155-156).

**Acute Effects of Hydromorphone:** Participants will ingest medication under staff supervision and complete a battery of self-report, physiological, and cortisol measures will be collected prior to dosing and up to 15 time points post-dose (up to 6 hours). During the final assessment each day, participants will complete a Drug vs. Money Questionnaire modeled from the Multiple Choice Procedure to indicate the dollar value they would place upon the drug received and this measure will be repeated immediately prior to the next day's drug administration. These experimental procedures are consistent with those used in a previous study by our group (110). Participants will be discharged from the study on the final day after completing the final study assessment and a field sobriety test that indicates no persistent opioid effects. We will conduct a follow-up phone call with participants the day following discharge to document any adverse events and to administer the final Drug vs. Money Questionnaire.

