## 7. Study Statistics

a. Primary outcome variables. The primary outcome variables are self-reported ratings of drug high and liking, changes in pupil diameter and blood pressure, pain threshold on 2 laboratory measures of pain, and analgesic efficacy in response to laboratory-induced pain. We expect that individuals with the minor allele of the A118G SNP and other

tagging SNPs across the OPRM1 gene will find hydromorphone more reinforcing (e.g., higher self-report ratings of high and drug-liking) and exhibit greater opioid-induced physiological changes (e.g., pupil diameter, blood pressure). Research also suggests the OPRM1 gene may also confer greater sensitivity to the negative effects of opioids, which may be observed as measuring greater ratings of nausea. We also hypothesize the minor allele and other tagging SNPs across the OPRM1 gene will produce higher pain threshold on 2 laboratory measures of pain, and lower analgesic efficacy in response to laboratory induced pain.

**b. Secondary outcome variables.** Decreases in cortisol levels as a function of the degree of pleasant effects of hydromorphone and painful stimuli, delay-discounting curves, and the effect of sex on all outcome measures. We hypothesize that individuals with the minor alleles will have greater decreases in cortisol levels as a function of the degree of pleasant effects of hydromorphone, lower cortisol in response to painful stimuli, and steeper discounting curves on a delay-discounting task. Finally, although we expect that the A118G will be associated with these effects, we hypothesize that several of the additional OPRM1 tagging SNPs will contribute to effect magnitude.

**c. Statistical plan including sample size justification and interim data analysis:** The aims of the proposed study will explore the impact of genetic variation across the OPRM1 gene on hydromorphone response. There are specific steps we describe below to assure that we interrogate all known functional variation across the OPRM1 gene, adequately cover all other variation using appropriately selected tagging SNPs, prevent spurious associations due to population stratification by accounting for local ancestry, and properly control the Type I error rate.

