**Association Model:** Our primary goal is to demonstrate the impact of SNP variation across OPRM1 on variability in response to hydromorphone across time and dose. Association analyses will be performed by modeling genotype at each SNP in a general linear model. In its simplest form this test, commonly termed the measured genotype analysis (137), models the influence of genotypic variation at a given locus on variation in the quantitative trait, essentially a one-way Analysis of Variance (ANOVA). This approach provides a distinct advantage in that it can easily be extended to a two-way ANOVA to model genotype effects across 3 different doses of drug. In addition, the flexibility of the GLM allows incorporation of ancestry covariates and environmental moderators or mediators. We will examine the impact of OPRM1 at each time-point in separate analyses and account for the multiple testing using LD-adjusted Bonferroni correction (see below).

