**Analysis of pain testing sessions:** We hypothesize that OPRM1 SNP variants will exhibit greater pressure pain thresholds, greater CPM efficiency, lower hydromorphone-related analgesia, and lower cortisol stress response than participants with the major allele, and that results will be positively correlated with response to self-report and physiologically-mediated hydromorphone drug effects collected during days 3-5. Pressure pain threshold will be estimated by averaging the results of the 2 administrations to radiobrachialis and quadriceps muscle groups. We will generate a CPM index for each participant [(mean pressure pain threshold during cold pressor)/(mean pressure pain threshold prior to cold pressor)] x 100 (90). These values will provide a quantitative measure of percent change in the test stimulus (i.e., pressure point threshold). Mixed effects regression models with a random intercept will be used to compare dependent variables (pressure pain threshold, DNIC threshold, DNIC index) as a function of within-subject drug effects (placebo vs. hydromorphone), and between-subject effects of OPRM1 SNP analysis will be conducted as specified in Aim 1. Gender, age, and race have been associated with response to pain and the CPM test (146-148). Gender will be evaluated using independent subgroup analyses and age and race will be included as covariates. Finally, subscale scores of self-report measures of pain and coping strategies will be compared between the two genotype groups using independent samples t-tests, and drug identification data will be compared using a chi-square for each drug condition. We expect that both experimental manipulations will induce pain in the minor and major allele groups, and that participants with the minor allele will demonstrate lower sensitivity to pain (e.g., greater pressure pain magnitudes), lower NRS ratings of pain, lower cortisol response to painful stimuli, and lower analgesic relief from hydromorphone compared to the major allele participants.

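### No association model pre-specifies the pre-dose value as a covariate, and the reference point for change in pupil diameter, blood pressure and cortisol is not defined

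*Combined protocol and SAP*

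**What the plan says.** Section 4a (Acute Effects of Hydromorphone) describes the measurement schedule: self-report, physiological and "cortisol measures will be collected prior to dosing and up to 15 time points post-dose (up to 6 hours"). The protocol describes this battery for the daily dosing sessions; that a pre-dose value exists for each of the four sessions is inferred from that description.

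Section 7a lists the primary outcomes. Two are worded as ratings, "self-reported ratings of drug high and liking", and two as differences from something, "changes in pupil diameter and blood pressure". Section 7b words the cortisol outcome as "Decreases in cortisol levels as a function of the degree of pleasant effects of hydromorphone and painful stimuli". In no case is the reference value given.

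Section 7c (Association Model) says that "Association analyses will be performed by modeling genotype at each SNP in a general linear model", that "the flexibility of the GLM allows incorporation of ancestry covariates and environmental moderators or mediators", and that "We will examine the impact of OPRM1 at each time-point in separate analyses". The paragraph on pain testing sessions adds that "age and race will be included as covariates", for the pain models. Section 5 allows birth control as a possible covariate. A pre-dose value appears in none of these lists.

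**The concern.** There are two linked gaps.

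First, change could be measured from the same morning's pre-dose reading or from the placebo session. These are different outcome variables with different error variances, and two of the affected outcomes are primary. With many SNPs, up to 15 post-dose times and several outcomes, leaving this open allows the choice to be made after the data are seen.

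Second, where pre- and post-dose values of one person are correlated, entering the pre-dose value as a covariate is the more precise use of it. Precision is scarce in a study of 100 completers (50 per sex) tested at alpha 0.001. A simple change score can even be noisier than ignoring the pre-dose value if the correlation is low. For self-report ratings, the plan gives no baseline handling at all.

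**Working it through.** **Inputs from the plan (Section 7c, Power and Correction for Multiple Testing).** N = 100 completers or 50 per sex; alpha 0.001 (0.05/50); more than 80% power claimed for Cohen's d of about 0.45 and 0.67.

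**Assumptions, not in the documents.** Equal pre- and post-dose SDs (set to 1); pre/post correlation r of 0.5 to 0.8; two equal genotype groups; a two-sided test; one comparison at one time point.

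**The plan's own figure.** For two groups of 50 and d = 0.45, the noncentrality is 0.45 × √100 / 2 = 2.25 against a normal critical value of 3.29. Power is 14.9% (13.5% with the noncentral t). For two groups of 25 and d = 0.67 it is 17.8% (14.6%). The stated figure of more than 80% does not reproduce from a single comparison. Averaging three active doses with no between-dose correlation gives 72.8% and 79.2% two-sided, or 79.0% and 84.4% one-sided; at a between-dose correlation of 0.5 the two-sided values fall to 29.6% and 34.9%. That is a separate issue. It matters here only because it sets the level from which any gain starts.

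**Residual variance under three ways of using the pre-dose value.**

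- Post-dose value alone: 1
- Change from pre-dose: 2(1 − r)
- Pre-dose value as covariate: 1 − r²

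Covariate against change: (1 − r²) / [2(1 − r)] = (1 + r)/2.

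| r | Change | Covariate | Cut against change | Cut against raw post-dose |
|---|---|---|---|---|
| 0.3 | 1.40 | 0.91 | 35% | 9% |
| 0.5 | 1.00 | 0.75 | 25% | 25% |
| 0.7 | 0.60 | 0.51 | 15% | 49% |
| 0.8 | 0.40 | 0.36 | 10% | 64% |

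For r of 0.5 to 0.8 the cut against a change score is 25% down to 10%, equivalent to 1/0.75 − 1 = 33% down to 1/0.90 − 1 = 11% more participants. Below r = 0.5 the change score has a larger variance than the raw post-dose value.

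**Effect on power at the plan's effect size.** Take d = 0.45 in change-score SDs, 50 against 50, noncentral t. The change score gives 13.5%. With the covariate the effective d is 0.45/√((1 + r)/2):

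- r = 0.5: 0.45/√0.75 = 0.520, power 22%
- r = 0.8: 0.45/√0.90 = 0.474, power 16%

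For comparison, a test that already has 80% power on the change score (d = 0.85) would rise to 93% at r = 0.5 and 86% at r = 0.8. That effect is nearly twice the one the plan is built on.

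**What would be needed to reach 80%.** If d = 0.45 is instead read in raw post-dose SDs, the detectable d at 80% power is about 0.826 (normal approximation). The covariate would have to explain 1 − (0.45/0.826)² = 0.70 of the variance, that is, r of about 0.84.

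**Sensitivity to equal SDs.** With post/pre SD ratio k, the change variance is k² + 1 − 2rk and the covariate variance is k²(1 − r²). At k = 0.6 and r = 0.8 the cut is 68%; at k = 1.2 and r = 0.8 it is about 0%. The 10-25% range therefore depends on the equal-SD assumption, although in this model the covariate never does worse, apart from one degree of freedom.

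**The case against.** A reader might infer that the pre-dose data go unused and that all stable between-person differences fall into the error term. The documents do not support that. Pupil diameter and blood pressure are named as changes and cortisol as decreases, which implies a reference value; it is undefined, not absent. A change from pre-dose removes stable person-level differences by subtraction, and so does a contrast with the within-person placebo session, which Section 4e includes as a comparison for opioid effects. The 25-64% cut against raw post-dose values therefore applies only if the plan uses neither.

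Nor is ancestry the only covariate named: Section 7c also allows environmental moderators or mediators, the pain models add age and race, and Section 5 mentions birth control. A flexible model is not a pre-specified one, however, and none of these is a pre-dose value.

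The strongest point against adjustment is that genotype is not randomised. Section 3 cites A118G associations with receptor availability and stress-hormone response, so an effect on pre-dose levels is plausible. In that case the adjusted and change-score analyses answer different questions. This stands, and it is why both should be shown.

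The gain for high may also be negligible if pre-dose ratings sit near zero (an assumption). Ratings such as like how I feel or feel sleepy, listed under Session Measures, could be non-zero before dosing.

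**Conclusion.** The point holds as a gap in specification with a modest cost in precision. The reference for change is undefined for two primary outcomes and for cortisol, and no model pre-specifies the pre-dose value as a covariate. With equal SDs and r of 0.5 to 0.8, adjustment cuts error variance by 10-25% against a change from pre-dose. The correlation and the SDs are not in the documents, so the loss cannot be fixed to one number, and a placebo contrast, if used, would already capture part of the gain.

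It would be wrong to conclude that baseline adjustment rescues the power claim. At d of about 0.45 in change-score units, power moves from about 14% to 16-22% in a single comparison, far from the stated 80%. This is a worthwhile, inexpensive improvement, not a flaw that by itself invalidates the analysis.

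**What to change.** In Sections 7a and 7b, state for each outcome whether change is measured from the same-session pre-dose value or from the placebo session. In Section 7c, pre-specify the same-session pre-dose value as a covariate in the models for pupil diameter, blood pressure, cortisol and any rating not near zero before dosing. Report the change-score analysis alongside, and state that the two may differ if genotype shifts pre-dose levels.

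The cost is a short addition to the text, one degree of freedom per model and a second set of results. The pre-dose battery is already planned, so participants carry no added burden. The price is one of interpretation: with a non-randomised genotype, the choice of primary analysis is also a choice of question and should be made before the data are examined.

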#### Study Measures to Establish Eligibility and Characterize Sample:

- BPRU Demographic Questionnaire: A questionnaire designed by us to document standardized demographic items (e.g., age, gender, marital status).
- Alcohol/Drug subscale of the Addiction Severity Index (111): A 31-question subscale that assess past 30 day and life-time use of drugs, history of treatment, and interest in treatment. Subscales provide a measure of severity.
- MINI International Neuropsychiatric Instrument: A standardized semi-structured diagnostic interview assesses participants for evidence of psychiatric disorders. The MINI will be used to verify that participants do not meet DSM-IV-TR dependence on alcohol and/or drugs.
- NIDA Genetic Questionnaire: This questionnaire lists several specific questions recommended by the NIDA Genetic Council for any study conducting research on the pharmacogenetics of substance abuse.
- Brief Pain Inventory (BPI; (112)): A 9-item widely-used, standardized, self-report measure to characterize the presence and severity of pain, as well as the interference of pain in every-day activities. The BPI has been modified to be appropriate for self-administration, and for use in an opioid-treatment population.
- Fagerström Test for Nicotine Dependence (FTND; (113)): A 6-item measure to determine presence of smoking and severity of nicotine dependence.
- Profile of Mood States-2 (114): A 65-item questionnaire that is a standardized and normed measure of personality that yields a measures of different personality features (anger-hostility, confusion, depression, fatigue, tension-anxiety, vigor, and friendliness).
- Barratt Impulsiveness Scale (115): A 30-item, widely used measure of impulsivity that will provide a self-report comparison to the delay discounting test of impulsivity.
- The Positive and Negative Effect Scale (PANAS; (116)): A 20-item self-report measure to characterize positive and negative emotional responses to pain.
- Coping Strategies Questionnaire- Short Form (CSQ Short Form; (117)): A 16-item self-report measure to characterize emotional response to pain and perceived efficacy of coping strategies.
- Pain Catastrophizing Scale (PCS; (118)): A 14-item self-report measure to characterize the emotional response to pain, with particular emphasis on anxiety and/or fear of pain.
- McGill Pain Questionnaire-Short Form (MPQ Short Form; (119)): A 15-item widely-used standardized, self-report measure to characterize presence and severity of pain.

#### Session Measures:

- Clinical Opiate Withdrawal Scale (120): A widely used, 11-item observer-rating of opioid withdrawal symptoms.
- Vital Signs: We will assess blood pressure, pulse, respiration, and oxygen saturation.
- Pupillary Diameter: Pupil size will be assessed using an electronic Neuroptics Pupilometer
- Visual Analog Rating Scales: Participants will rate the following items on a scale of 0 (none at all) to 100 (strongest possible): good effects, bad effects, high, withdrawal, sick, like how I feel, nausea, sedation, feel sleepy
- Opioid Agonist/Antagonist Rating Scale: This questionnaire assesses positive and negative effects of opioids.
- Drug vs. Money Questionnaire: This questionnaire is a frequently used measure to assess relative monetary value of a drug and is being used to assess relative reinforcing effects of the drug compared to hypothetical monetary values.
- Neurocognitive Assessment: A battery of tasks designed to measure neurocognitive performance that has been developed by our research unit will be adapted for this study. Functions to be tested include psychomotor speed/pattern recognition (e.g. digit symbol substitution) and short-term/working memory and focused attention (e.g. N-back task).
- Hypothetical Purchase Task: This questionnaire is used to measure the abuse liability of drugs by assessing the magnitude and persistence of demand for a given drug under cost constraints. Participants indicate how many drug units (i.e., capsules) they would purchase at increasing price points for a 24-hour period of use.

#### Delay Discounting (DD):

- We will administer monetary and commodity-based DD tasks via computer to participants during the Screening visit, and each session day during peak drug effects (30 minutes). DD for \$100 will be assessed using a computer program developed by Co-investigator [name] that has been utilized in numerous studies (121-126) and will be quantified using the area-under-the-curve (AUC) method (127). The hypothesized results are that the minor allele of the A118G and other minor alleles of OPRM1 tagging SNPs will be associated with steeper discounting curves (less AUC).

**Genetic Analysis:** Genotyping will be supervised by Co-Investigator [name]. All blood genetic samples will be collected and transported to the main Hopkins hospital on a weekly basis for analysis. A chain of custody will be kept to ensure proper delivery and receipt of all samples. No participants name will be written on any genetic sample and participants will not be informed of the results of the genetic testing.

For all SNPs across the OPRM1 gene including the A118G and ancestral markers (see Statistical Analysis), genotyping will be performed with GoldenGate Genotyping Assay. The DNA sample used in this assay is activated for binding to paramagnetic particles. This activation step is a highly robust process that requires a minimum input of DNA (250ng at 50ng/μl). Depending upon the multiplex level, this equates to only 160pg of DNA per SNP genotype call. Assay oligonucleotides, hybridization buffer, and paramagnetic particles are then combined with the activated DNA in the hybridization. Three oligonucleotides are designed for each SNP locus. Two oligos are specific to each allele of the SNP site, called the Allele-Specific Oligos (ASOs). A third oligo that hybridizes several bases downstream from the SNP site is the Locus-Specific Oligo (LSO). All three oligonucleotide sequences contain regions of genomic complementarity and universal PCR primer sites; the LSO also contains a unique address sequence that targets a particular bead type. Up to 1,536 SNPs may be interrogated simultaneously in this manner using GoldenGate technology. During the primer hybridization process, the assay oligonucleotides hybridize to the genomic DNA sample bound to paramagnetic particles. Because hybridization occurs prior to any amplification steps, no amplification bias can be introduced into the assay. Following hybridization, several wash steps are performed, reducing noise by removing excess and mis-hybridized oligonucleotides. Extension of the appropriate ASO and ligation of the extended product to the LSO joins information about the genotype present at the SNP site to the address sequence on the LSO. These joined, full-length products provide a template for PCR using universal PCR primers. Universal PCR primers P1 and P2 are Cy3- and Cy5-labeled. After downstream-processing 5 the single-stranded, dye-labeled DNAs are hybridized to their complement bead type through their unique address sequences. Hybridization of the GoldenGate Assay products onto the Array Matrix or BeadChip allows for the separation of the assay products in solution, onto a solid surface for individual SNP genotype readout. After hybridization, the BeadArray Reader is used to analyze fluorescence signal on the Sentrix Array Matrix or BeadChip, which is in turn analyzed using software for automated genotype clustering and calling.

- b. Study duration and number of study visits required of research participants.

Participants will complete a Screening visit and will be enrolled in this study for a total of 5 days (Admission Day + 4 session days; Figure 1).

- c. Blinding, including justification for blinding or not blinding the trial, if applicable.

Participants will be informed in the consent will that the study drug may consist of one or more of numerous different drug classes (e.g., opioids, stimulants, over-the-counter medications). This is a common practice in laboratory-based studies of drug effects, a practice that we have followed for several years, and one that is recommended in peer-reviewed guidelines for abuse liability testing (103, 104). We will inform participants of the risks associated with hydromorphone (without revealing the drug type) in the consent form so they will be able to make an informed decision about study participation. Participants will receive double-blind oral doses of hydromorphone or placebo during the study to prevent expectancy effects and enable a rigorous evaluation of opioid administration on a variety of clinically-relevant outcome measures. Staff members will also be blinded to what study drug is being provided.

- d. Justification of why participants will not receive routine care or will have current therapy stopped.

N/A

- e. Justification for inclusion of a placebo or non-treatment group.

A placebo condition has been included as a comparison for opioid-induced effects.

- f. Definition of treatment failure or participant removal criteria.

Participants will be removed from study participation if they ask to be removed, if they exhibit an allergic reaction to the study drug, if they fail to comply with the requirements of the study, or if new information becomes available that suggests that continued study participation may put them at increased risk of adverse events.

- g. Description of what happens to participants receiving therapy when study ends or if a participant’s participation in the study ends prematurely.

Participants are healthy controls. They are not treatment-seeking and do not have any underlying medical condition that would warrant continued treatment upon completing the study. Participants will be informed they can agree to begin the study now and withdraw later without any penalty. Participants who request to discharge from the study prior to completing the study will be assisted with contacting medical professionals upon request from the participant.

